Measure Yourself Medical Outcome Profile (MYMOP) is a patient centered outcome measure that allows for the participant to self-select their top health concern(s) or symptom(s) they are dealing with in their own words. The participant can also choose an activity that is limited by that health concern. The participant is then asked about their own general wellbeing. Each of these questions is scored on a 0-6 scale. The medications that the participant is taking related to the specific symptoms and their desire to cut down the medication is also recorded.

Scoring of the MYMOP is an average of all of the profile questions answered. Participants only have to choose one symptom and answer the well-being profile question. If a second related symptom and activity level are identified all of the scores are included in the average final score.

MYMOP has been shown to be an effective outcome measurement for health concerns, especially in a diverse population and has more sensitivity to change compared to the SF-36.^{29,30}

D.4.2.2. Secondary Measure: NUNM Multi-system Symptom/Adverse Events Questionnaire

The NUNM Multi-system Symptom/Adverse Event Questionnaire is a standardized ninety-one point monitoring form that requires asking questions pertaining to the following organ systems: eyes/ears/nose/throat, gastrointestinal, neurological/ musculoskeletal, psychological/general, cardiopulmonary, skin, genitourinary and whole body systems.

Table 3. Grading of Items on the NUNM Adverse Event Monitoring Form	
Grade	Definition
0=Not Present	No AE, Function within normal limits
1=Mild; asymptomatic or mild symptoms; clinical or diagnostic observations only; no intervention	No intervention; asymptomatic lab or radiographic findings; marginal clinical significance
2=Moderate; minimal, local or noninvasive intervention indicated	AE limited activities of daily living (ADLS)
3=Severe or medically significant but not immediately life-threatening	AE significantly limited basic self-care, AE required initial hospitalization or prolongation of hospitalization
4=Life-threatening	Life-threatening consequences AE
5=Fatal	Fatal AE

Changes in a current symptom(s) by a grade of 2 or higher, or a new symptom(s) graded 2 or higher will be included in analysis to compare symptom changes between groups.

Protocol

Study Title: Methylation Diet and Lifestyle (MDL) Study

PI: [name], ND, MPH and [name], ND

IRB #: RB100217

[figure not shown]
Approval Date: 2.9.18

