The following procedures, evaluation and/or assessments will be obtained at Study Visit 2:

- Weight
- Vital signs including heart rate, blood pressure, respiration rate and temperature
- Questionnaires including Lifestyle Habits, PROMIS-29, MYMOP, MSQ, and NUNM Adverse Events, VioScreen
- Blood draw to collect 2 tubes of blood
- Saliva sample
- If in intervention group, will receive study supplements for remaining 4 weeks of study
- Case report form completed by study staff

Study Visit 3 (Week 9)

The following procedures, evaluation and/or assessments will be obtained at Study Visit 3:

- Weight
- Waist-to-hip ratio will be calculated as previous defined in Study Visit 1
- Vital signs including heart rate, blood pressure, respiration rate and temperature.
- Questionnaires including Lifestyle Habits, PROMIS-29, MYMOP, MSQ, and NUNM Adverse Events, VioScreen
- Blood draw to collect 2 tubes of blood
- Saliva sample
- If in intervention group, return unused supplements
- Case report form completed by study staff

Protocol

Study Title: Methylation Diet and Lifestyle (MDL) Study

PI: [name], ND, MPH and [name], ND

IRB #: RB100217

Approval Date: 2.9.18

Ver. 1.1

D.5.9. Educational Webinars

Weekly, live webinars will provide information on the diet, exercise, stress management, and lifestyle recommendations. Prior to initiating any of these changes, an introductory webinar will provide an overview of the study intervention. An additional webinar will provide detailed instruction on how to access and utilize two electronic applications – MBody360 and Stress Free Now. All webinars will be delivered via Zoom, a free online communication application.

Refer to Appendix C for detailed information on webinar content

D.6. Study Withdrawal and/or Early Termination

Participants will be informed that they have the right to withdraw from the study at any time, without affecting their relationship with NUNM. Participants may also be discontinued from the study if the investigators determine it is in the best interest of the participant.

Information about study withdrawal or premature discontinuation from the study will be captured throughout the study. Study withdrawal or premature discontinuation will be categorized as follows:

- Participant began taking an excluded medication or supplement

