- The Principal/Clinical Investigator decided that withdrawal/discontinuation was in the best interest of the participant due to an adverse event, non-compliance, or another reason
- The participant requests withdrawal from the study for reasons other than above
- The participant failed to return for study visits

If a participant withdraws before the second visit, they will be replaced, however participants who withdraw between the second and third visits will not be replaced. Every effort will be made to collect a final salivary sample and all final labs from all participants, even if they withdraw from the study early.

D.7. Study Products

D.7.1. PhytoGanix (tropical fruit flavor)

Organic Superfruits & Greens Powder Drink Mix is a food-based phytonutrient blend designed to support intestinal health and immune function.

Protocol

Study Title: Methylation Diet and Lifestyle (MDL) Study

PI: [name], ND, MPH and [name], ND

IRB #: RB100217

Approval Date: 2.9.18

Ver. 1.1

Serving Size: 1 Scoop (10.4 grams)

Ingredient	Amount per serving
Calories	40
Total Carbohydrate	9 g
Dietary Fiber	1 g
Sugars	1 g
Protein	1 g
Vitamin C (as ascorbic acid)	100 mg
Calcium	20 mg
Iron	1.4 mg
Sodium	30 mg
Organic Seed and Prebiotic Blend:	5.53 g
Isomalto-Oligosaccharide, Flax Seed Powder, Chia Seed Powder, Quinoa (Chenopodium quinoa Willd.) Sprout Powder	
Organic Veggie Blend:	2.35 g
Spirulina Whole Algae Powder, Carrot Root Powder, Broccoli Head Powder, Cauliflower Head Powder, Spinach Leaf Powder, Parsley Leaf Powder, Bamboo Shoot Extract, Beet Root Powder	
Organic Fruit Blend:	1.2 g
Apple Fruit Powder, Pineapple Fruit Powder, Strawberry Fruit Powder, Raspberry Fruit Powder, Blackberry Fruit Powder, Blueberry Fruit Powder	
Herbal Support Blend:	300 mg
Milk Thistle Seed Extract, Turmeric Rhizome Extract, Green Tea Leaf Extract, Reishi Mushroom Whole Plant Powder, Maitake Mushroom Whole Plant Powder, Shiitake Mushroom Whole Plant Powder, Japanese Knotweed Root Extract, Quercetin Dihydrate, Organic Maca Root Powder, Organic Cassia Bark Powder, Dong Quai Root Powder, Ginger Root Powder, Garlic Bulb Powder	
Enzyme Blend (including protease, amylase, lipase, and cellulase)	200 mg
Lactobacillus acidophilus VK3 Strain	200 mg

Protocol

Study Title: Methylation Diet and Lifestyle (MDL) Study

PI: [name], ND, MPH and [name], ND

IRB #: RB100217

Approval Date: 2.9.18

Ver. 1.1

D.7.2. UltraFlora Intensive Care

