If an Adverse event (AE) is reported at Study Visit 1 or Study Visit 2, the Study Coordinator will contact the CI and/or the PI as soon as possible, i.e., during the appointment, for AEs graded as “moderate” or more severe (Grade 3 or higher). If the Study Coordinator is unable to reach the CI/PI within the appointment, the participant will be contacted by the PI as soon as possible within the same day. The Study Coordinator and CI will complete the “Standardized Adverse Events Questionnaire: Spontaneous Reporting” form (Appendix A) in order to capture details regarding the adverse event and any action taken.

If a participant calls the Study Coordinator or the Principal/Clinical Investigator to report AEs, a similar procedure will be followed, which will include completion of the “Standardized Adverse Events Questionnaire: Spontaneous Reporting” form.

G.3.1. Risk Classification: Low

All procedures are considered “low risk” as per the NUNM Helfgott Research Institute Procedure/Intervention Risk Classification list. These low-risk procedures include administering

Protocol

Study Title: Methylation Diet and Lifestyle (MDL) Study

PI: [name], ND, MPH and [name], ND

IRB #: RB100217

Approval Date: 2.9.18

Ver. 1.1

questionnaires, and venipuncture/blood draws on non-pregnant adults. Participants will be told about any new information that may affect their willingness to participate in the study.

G.3.2. Reporting to the NUNM Institutional Review Board

All adverse events will be recorded in the Adverse Event Log. Anticipated adverse events will be reported to IRB during continuing review. Unanticipated problems will be reported to IRB within 10 working days of the investigators being notified of the event. Serious adverse events will be reported to IRB within 24 hours of the investigators being notified of the event.

G.3.3. Adverse Event Definitions

Adverse Event (AE): Any untoward medical occurrence in a clinical investigation subject. An AE can therefore be an unfavorable and unintended sign (including abnormal laboratory findings), symptoms (nausea and loose stools), or disease temporally associated with the study, whether or not related to the study procedure, or a worsening of a pre-existing condition or illness.

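### G.3's trigger for prompt investigator contact says moderate but gives Grade 3, while Table 3 makes moderate Grade 2, so the rule contradicts itself for Grade 2 events

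*Protocol*

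**What the plan says.** The rule for adverse events raised at a visit is in Protocol G.3. It opens "If an Adverse event (AE) is reported at Study Visit 1 or Study Visit 2" and requires the Study Coordinator to contact the clinical investigator (CI) and/or principal investigator (PI) during the appointment for "AEs graded as “moderate” or more severe (Grade 3 or higher". If neither can be reached in that time, the PI is to contact the participant later the same day. The next sentence has the coordinator and the CI complete a spontaneous-reporting form.

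The grading scale is Table 3 in D.4.2.2, titled as the grading of items on the NUNM Adverse Event Monitoring Form. Two entries matter here:

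- "2=Moderate; minimal, local or noninvasive intervention indicated", defined as "AE limited activities of daily living (ADLS"
- "3=Severe or medically significant but not immediately life-threatening", defined by significantly limited basic self-care, or by initial or prolonged hospitalization

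D.5.8 lists the NUNM form at all three study visits in the same words: "Questionnaires including Lifestyle Habits, PROMIS-29, MYMOP, MSQ, and NUNM Adverse Events, VioScreen". At Visit 2 it also lists "If in intervention group, will receive study supplements for remaining 4 weeks of study". Under D.6, one recorded reason for leaving the study is an investigator's decision that "withdrawal/discontinuation was in the best interest of the participant due to an adverse event".

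**The concern.** G.3 is an instruction that a coordinator acts on with a participant in the room. Its threshold is stated once as a word and once as a number, and on the protocol's own scale the two do not agree. A coordinator who follows the word calls the investigator about a Grade 2 event. A coordinator who follows the number need not. Both would be complying with the protocol.

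The disputed grade is not trivial, because it covers events that limit daily activities. It is also plausibly where the rule would be used most. Participants are free of the listed major diagnoses, procedures are classed as low risk, and the product risks named in E.1.2 are gas, bloating, digestive upset and bowel change. Few such events would be expected to reach Table 3's Grade 3. That is inference, since the protocol gives no event counts.

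What is at stake is prompt medical review of one grade of event. It is not an efficacy result.

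**Working it through.** The point involves no sample-size, power or alpha figure, so the check is a direct comparison of texts.

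**Inputs.** The trigger word and trigger number come from G.3. The grade labels and definitions come from Table 3 (D.4.2.2). The visit schedule comes from D.5.8 and the start of dosing from D.7.3.

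**Step 1: apply both halves of the G.3 sentence to Table 3.**

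| Table 3 grade | Label | Contact by the word (moderate or more severe) | Contact by the number (Grade 3 or higher) |
|---|---|---|---|
| 1 | Mild | no | no |
| 2 | Moderate | **yes** | **no** |
| 3 | Severe | yes | yes |
| 4 | Life-threatening | yes | yes |
| 5 | Fatal | yes | yes |

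The word covers {2, 3, 4, 5} and the number covers {3, 4, 5}. The difference is {2}. The readings agree on every other grade.

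**Step 2: is Table 3 the scale that G.3 relies on?** Its title ties it to the NUNM adverse event form, and that form is completed at each visit, so an event found at a visit would be graded on it. The spontaneous-reporting form appears in G.3 after the contact step, as a way to record details and any action taken. It reads as following the trigger, not as supplying the grade.

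**Step 3: does other text show which threshold was meant?** D.4.2.2 uses Grade 2 as its cutoff for counting new symptoms in the between-group comparison. That makes Grade 2 the more coherent repair, but an analysis cutoff does not prove what was intended for safety contact.

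**Step 4: where does the ambiguity bear on the study products?**

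- Visit 1 is baseline. D.7.3 tells participants to wait until after the introductory webinar before taking supplements, so regular dosing has not begun.
- Visit 2 falls during dosing and is named in the rule.
- Visit 3 is when unused product is returned, and the rule does not name it.

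Of the two visits named, only Visit 2 is on treatment.

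**Step 5: do the other safety provisions settle the threshold?**

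- The same-day PI call is the fallback when the first contact fails, so it depends on the same trigger.
- Reports by telephone follow a similar procedure, which sets no separate threshold.
- E.2.2 says monitoring runs throughout the study but gives no grade.
- G.3.2 requires every event to be logged and sets timelines for IRB reporting, but does not say when the investigator must be called.

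**The case against.** The mismatch itself has no good answer in the text. The case on the other side concerns its consequences, and much of it stands.

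- **The CI helps complete the spontaneous-reporting form.** That sentence in G.3 states no grade limit. If it applies to any event reported at the visit, the CI learns of a Grade 2 event under either reading. It can equally be read as inheriting the trigger, and it gives no timing. It softens the effect but does not restore a same-day requirement.
- **Re-supply at Visit 2.** A reader might infer that the ambiguity decides whether a Grade 2 event reaches the investigator before the second batch of supplements is handed out. The documents do not support this. The Visit 2 procedures are an unordered list, and even the stricter reading asks only for contact during the appointment, with later that day as the fallback. D.6 likewise does not tie the discontinuation decision to same-appointment contact.
- **The setting is low risk.** Ingredients are described as generally recognized as safe, all events are logged, and serious events go to the IRB within 24 hours of the investigators being notified. This limits the likely harm but does not settle the threshold.
- **Another scale may exist.** The spontaneous-reporting form is not in the text at hand, so a scale on which moderate is Grade 3 cannot be excluded. Nothing in the protocol states one.
- **Visit 3 is a separate matter.** The same form is completed there but the in-person rule does not name the visit. A reader might infer that events first raised at Visit 3 go unhandled. They do not: logging and IRB reporting are not tied to a visit, and dosing is ending. The omission adds no weight to the grade mismatch.

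**Conclusion.** G.3 is wrong as written. Its word and its number cannot both hold on Table 3, and they disagree for exactly one grade, Grade 2. Read by the number, the rule leaves events that limit daily activities outside required same-day investigator contact. For product safety the effect is mainly on Grade 2 events reported in person at Visit 2.

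How many events that would be cannot be estimated, because the protocol gives no expected counts. The intended threshold cannot be determined from the document either, and either one would be an acceptable design if stated consistently. The conclusion assumes that events at visits are graded on Table 3, the only scale shown.

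A reader might also infer that trial results are affected, since D.4.2.2 uses the same grades as an outcome. They are not. That comparison takes grades from the questionnaire, whoever is telephoned, and the primary analysis uses PROMIS-29 T-scores. This is a narrow error in a safety instruction that should be corrected.

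**What to change.** In G.3, replace the trigger with *moderate or more severe (Grade 2 or higher)*, which agrees with Table 3. If the investigators confirm that the higher threshold was meant, write *severe or worse (Grade 3 or higher)* instead. If the spontaneous-reporting form carries its own scale, check it against Table 3 at the same time.

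As a minor separate edit, extend the opening of G.3 to Study Visits 1, 2 and 3.

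The cost is two wording changes in one section and, with the Grade 2 threshold, at most a few more coordinator calls to the investigator. Sample size, visit schedule and analysis do not change.

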Understanding that environmental factors can potently and sometimes rapidly, favorably or negatively influence epigenetic expression, a short-term diet and lifestyle intervention may significantly augment DNA methylation expression.

The purpose of this study is to evaluate a 9-week diet and lifestyle intervention on patient-reported quality of life, symptoms, and DNA and biochemical methylation-related biomarkers in healthy males ages 50-72.

B. SPECIFIC AIMS

B.1 Primary Aim:

To evaluate a 9-week diet and lifestyle intervention on patient-reported quality of life.

Hypothesis: Quality of life will improve as a result a 9-week diet and lifestyle intervention, relative to a wait-list control condition.

Outcome measure: Changes in patient-reported quality of life, measured by the PROMIS-29 (Patient-Reported Outcomes Measurement Information System-29) questionnaire.

B.2 Secondary Aim:

To evaluate changes in patient-reported symptoms after a 9-week diet and lifestyle intervention.

Hypothesis: Severity of patient-reported symptoms will decrease following a 9-week diet and lifestyle intervention.

Outcome measures: Changes in patient-reported symptoms, measured by the MYMOP (Measure Yourself Medical Outcome Profile) questionnaire, NUNM Multi-system side effects/symptoms questionnaire, and the Medical Symptom Questionnaire (MSQ).

Protocol

Study Title: Methylation Diet and Lifestyle (MDL) Study

PI: [name], ND, MPH and [name], ND

IRB #: RB100217

Approval Date: 2.9.18

Ver. 1.1

B.3 Tertiary Aim:

To assess changes in methylation at CpG sites of DNA after a 9-week diet and lifestyle intervention.

Hypothesis: Methylation at CpG sites associated with chronic inflammation will change after the 9-week diet and lifestyle intervention.

Outcome measure: Number of CpG methylation sites, measured by the Infinium MethylationEPIC Kit (Illumina, Inc.)

B.4 Exploratory Aims:

To evaluate changes in biomarkers associated with methylation.

Outcome measures: Changes in the methylation related biomarkers as measured by Doctor's Data Methylation Index Panel, Methylation Profile, and Folate Vitamer Panel.

C. BACKGROUND AND SIGNIFICANCE

C.1. Methylation background and significance

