This study is a preliminary randomized control trial evaluating a 9-week diet and lifestyle intervention on quality of life, patient-reported symptoms, and biomarkers associated with methylation. We will recruit forty-eight participants with 24 randomized to each study group. Refer to Figure 1 for an overview of the study flow.

Figure 1. Study Flow Overview

D.2 Study Intervention

Study participants will be randomized into an intervention or control group. The intervention group will undergo a 3-week washout period following the discontinuation of any non-medically required nutrition or herbal supplements. The intervention group will follow detailed diet and lifestyle recommendations over a 9-week period. Two webinars at the start of the

Protocol

Study Title: Methylation Diet and Lifestyle (MDL) Study

PI: [name], ND, MPH and [name], ND

IRB #: RB100217

Approval Date: 2.9.18

Ver. 1.1

intervention phase will provide information to participants on proper food and exercise choices, as well as how to access and use the required electronic resources (apps).

The control group will undergo the same testing measures as the intervention group, but will not have access to the education information or be instructed to change diet or lifestyle factors. They will have access to the information after the study is complete.

D.2.1 Diet Recommendations

Specific dietary guidelines will be outlined for participants and should include the following:

Per week	Per day

3 servings of liver
 
 • (1 serving = 3 oz) • Choose preferably organic liver 
5-10 eggs
 
 • Ideally free-range, organic, omega-3 enriched 	
2 cups of dark leafy greens
 
 • Measured raw, chopped, and packed • Including kale, Swiss chard, collards, spinach, dandelion, mustard greens • Does not include salad greens such as romaine, iceberg, Spring mix 
2 cups cruciferous vegetables
 
 • Measured raw, chopped, and packed • Including broccoli, cabbage, cauliflower, Brussels sprouts, bok choy, arugula, kale, watercress, rutabaga, kohlrabi, radish, turnip
General	

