Serious Adverse Event (SAE): Any untoward medical occurrence that results in death, is life-threatening, requires inpatient hospitalization or prolongation of existing hospitalization, results in persistent or significant disability or incapacity, or results in a congenital anomaly or birth defect. Other important medical events requiring medical or surgical intervention to prevent a serious outcome would also be considered SAEs.

Unanticipated Problems (UP): Any incident, experience, or outcome that meets all of the following criteria: 1) unexpected (in terms of nature, severity, or frequency) given (a) the research procedures that are described in the protocol-related documents, such as the IRB-approved research protocol and informed consent document; and (b) the characteristics of the subject population being studied; 2) related or possibly related to participation in the research and 3) suggests that the research places subjects or others at a greater risk of harm (including physical, psychological, economic, or social harm) than was previously known or recognized.

G.4. Statistical Analysis

PROMIS 29 T-scores will be presented as mean (SD), for each group at each of the three data collection time points. For the primary aim, we will compare changes in PROMIS-29 T-scores between groups, using a linear mixed model with random intercept to test for a Group*Visit interaction. If there is a significant main effect, we will also present uncorrected contrasts comparing changes from baseline to Week 5, and from baseline to Week 9, between groups.

Although PROMIS T-scores are not particularly susceptible to extreme outliers, data will be examined for any outlying PROMIS scores or changes in PROMIS scores. If these scores are deemed to be in error, then they will be treated as missing in all analyses. Otherwise, scores

Protocol

Study Title: Methylation Diet and Lifestyle (MDL) Study

PI: [name], ND, MPH and [name], ND

IRB #: RB100217

Approval Date: 2.9.18

Ver. 1.1

will be retained in the main analysis; but we will conduct separate sensitivity analyses to test for effects of outlying data on results.

Mixed models incorporate all available data, without excluding any participants from analysis. Nevertheless, any participants who have baseline data only will be excluded from analysis. As an exploratory follow-up analysis, we will re-analyze changes from Week 1 to Week 9, using data from completers only.

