For the secondary aim, the total score of the MSQ will be analyzed similarly to PROMIS-29. Since MYMOP asks for two symptoms without distinction, we will classify each problem as either the *Primary* problem (the problem with the highest symptom rating at baseline; or, in the case of a tie, the first problem listed) or the *Secondary* problem. We will also calculate the *average* of the two problem scores, at each collection time point. If only one problem is listed, then this will be used as both the Primary and Average, for that individual, with Secondary score missing. Changes in MYMOP severity scores will be compared between groups using a non-parametric Mann-Whitney test. Separate comparisons will be made between changes over the first 4 weeks of the study and changes over the entire 9-week intervention period.

G.5 SPONSOR RESPONSIBILITIES FOR INTERVENTIONAL PRODUCT(S)

The sponsor, Metagenics, is responsible for supplying the interventional product(s) in accordance with Good Manufacturing Practices (GMP). These products will be fully characterized, properly coded and suitably packaged in a way to provide protection against deterioration with appropriate labelling. Sufficient samples of each batch and a record of analyses and characteristics will be kept by the sponsor for reference so that, if necessary, an independent laboratory is able to re-check the interventional product(s), e.g. for quality control or bioequivalence. Records of the quantities of interventional products supplied will be maintained with batch or serial numbers by sponsor. The sponsor will ensure that the investigator is able to establish a system within their institution for adequate and safe handling, storage, use during the course of the study and, if appropriate, return or destruction of the interventional product(s) upon completion of the study.

G.6 SPONSOR MONITORING

The sponsor, Metagenics, will appoint suitable and appropriately trained monitor(s) and clinical research support personnel to conduct regular site visits starting with recruitment and continuing on a schedule that is mutually agreed upon by the study coordinator and sponsor. Follow up information from these visits will be provided to site, sponsor and to Principal Investigators in a timely manner for their reference purposes.

Protocol

Study Title: Methylation Diet and Lifestyle (MDL) Study

PI: [name], ND, MPH and [name], ND

IRB #: RB100217

Approval Date: 2.9.18

Ver. 1.1

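### G.4 presents the model-based Week 5 and Week 9 group differences only after a significant test, so a null result would carry no confidence interval for the primary effect

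*Protocol*

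**What the plan says.** The primary hypothesis (B.1) is comparative: "Quality of life will improve as a result a 9-week diet and lifestyle intervention, relative to a wait-list control condition". For it, G.4 compares changes in PROMIS-29 T-scores between groups "using a linear mixed model with random intercept to test for a Group*Visit interaction". It then sets the reporting rule: "If there is a significant main effect, we will also present uncorrected contrasts comparing changes from baseline to Week 5", with the same for baseline to Week 9.

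Two outputs in G.4 carry no such condition. One is descriptive: "PROMIS 29 T-scores will be presented as mean (SD), for each group at each of the three data collection time points". The other is a follow-up: "As an exploratory follow-up analysis, we will re-analyze changes from Week 1 to Week 9, using data from completers only".

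The MSQ takes over the conditional rule: "For the secondary aim, the total score of the MSQ will be analyzed similarly to PROMIS-29". The MYMOP group comparisons, over the first 4 weeks and over the whole period, have no significance condition.

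On size and purpose, D.1 says "This study is a preliminary randomized control trial evaluating a 9-week diet and lifestyle intervention on quality of life" and "We will recruit forty-eight participants with 24 randomized to each study group". D.3.1 expects 40 evaluable men, and section F describes the output as proof-of-concept data.

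**The concern.** The difference between groups in change from baseline is the quantity that the primary hypothesis is about. The protocol itself decides when that quantity is shown, and it is shown only if a test succeeds. This is therefore a stated reporting rule, not a detail left open for a later analysis plan.

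In a small preliminary trial the estimate and its uncertainty are the most useful product, for planning a follow-on trial or for pooling. If the test fails, which is a likely outcome at this size unless the effect is large, the reader gets a test result without the interval that says which effects remain plausible. The primary outcome would also be reported on stricter terms than the MYMOP, a secondary one.

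**Working it through.** **1. What remains after a non-significant test**

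| Output in G.4 | Conditional? | Gives a difference in change? | Gives its interval? |
|---|---|---|---|
| Mean (SD) by group and visit | No | Yes, crude, by subtraction | No |
| Completers-only Week 1 to Week 9 | No | Yes, exploratory, no Week 5 | None promised |
| Model contrasts, Weeks 5 and 9 | Yes | Yes | Obtainable from the model |

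The visit SDs do not give the interval because SD(change)² = SD₁² + SD₉² − 2·r·SD₁·SD₉, and the within-person correlation r is not among the promised outputs. After dropout, the men behind each visit mean also differ.

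**2. Width of the interval that would be missing**

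Inputs: 40 evaluable men (D.3.1) with 1:1 allocation (D.1), so n = 20 per arm. The protocol gives no SD, r, alpha or target effect. Assumed: T-score SD 10, equal correlation r between visits, two-sided 5%.

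In the random-intercept model the residual variance is SD²(1 − r), so the standard error of the difference in change is SE = SD × √[4(1 − r)/n]. The half-width is t × SE, with t = 1.99 on 76 df.

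- r = 0.5: SE = 10 × √(4 × 0.5/20) = 3.16; half-width 6.3
- r = 0.6: SE = 10 × √(4 × 0.4/20) = 2.83; half-width 5.6
- r = 0.7: SE = 10 × √(4 × 0.3/20) = 2.45; half-width 4.9

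For example, a crude difference of 2 points would go with an interval of −4.3 to 8.3 at r = 0.5 and −2.9 to 6.9 at r = 0.7. With r unknown the reader cannot tell which. If r could be anything from 0 to 0.9, the same formula gives half-widths from 8.9 (1.99 × 4.47) down to 2.8 (1.99 × 1.41).

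**3. How often the contrasts would be withheld**

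This reads the condition as the 2-df Group*Visit test and assumes a Week 5 effect half the Week 9 effect. In simulation, the contrasts are presented in 12 to 18% of trials for a true Week 9 effect of 3 T-points and in 27 to 42% for 5 points (r 0.5 to 0.7). They would be withheld in 82 to 88% and 58 to 73%.

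**4. What the filter does to the contrasts that are shown**

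Each ratio is the mean Week 9 estimate among trials passing the test, divided by the true effect, at 20 per arm. The T-point rows assume SD 10 and a Week 5 effect half the Week 9 effect.

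| Condition | True Week 9 effect | Ratio, r = 0.5 | Ratio, r = 0.7 |
|---|---|---|---|
| Interaction | 3 points | 2.4 | 2.0 |
| Interaction | 5 points | 1.7 | 1.4 |
| Interaction | 8 points | 1.24 | 1.09 |
| Main effect (Group or Visit) | 3, 5 or 8 points | about 1.0 | about 1.0 |

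Over a wider range, a single t-test on change scores gives 3.4 at a true effect of 0.2 SD of change, 1.7 at 0.5, 1.19 at 0.8 and 1.02 at 1.2. The joint interaction test with r = 0.5 gives about 2.8 to 3.0 at 0.2 and 1.05 to 1.11 at 1.0, depending on the Week 5 effect.

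The main-effect rows are near 1 for a structural reason. In a balanced random-intercept design the Group effect (averaged over visits) and the Visit effect (averaged over groups) are both orthogonal to the group difference in change. Selecting on either leaves that difference unbiased. A main-effect condition still withholds the contrasts when it fails, and does so for a reason unrelated to the hypothesis.

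**The case against.** Four points can be made for the plan.

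- **A null trial is not left without any estimate.** This stands. The visit means allow a crude difference, and the completers-only analysis is unconditional. A reader might infer that a non-significant trial shows no effect at all; G.4 does not support that. What is missing is the model-based difference with its precision. The completers-only analysis does not replace it: it is exploratory, drops non-completers, omits Week 5 and promises no interval.

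- **The overstatement is not a property of the plan.** This largely stands. A reader might infer a fixed inflation, such as 1.4 to 2.4 times. That range needs the interaction reading and true effects of 3 to 5 T-points, neither of which the protocol fixes. It shrinks to about 1.1 to 1.25 at 8 points and vanishes under the literal wording.

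- **Unconditional presentation does not change the number in a significant trial.** This stands. Exaggeration among significant results comes from low power, and the contrast printed would be the same. The gain lies in the results that would otherwise be withheld.

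- **An overall test followed by uncorrected contrasts is a conventional protected procedure.** This is fair as regards significance claims, and that protection can be kept. It is not a reason to withhold estimates. Presenting every interval does mean that some may exclude zero when the overall test is not significant, so labelling is needed.

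**Conclusion.** The point holds as a reporting defect with a cheap remedy. G.4 withholds the model-based group differences in change at Weeks 5 and 9 unless a test is significant, for the PROMIS-29 and, by inheritance, for the MSQ. A null result would lack the interval needed to separate little effect from too little information. That interval would have a half-width of about 5 to 6 T-points, given the assumed SD of 10, r of 0.5 to 0.7 and 20 men per arm.

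Average overstatement of the presented estimates is a secondary consequence. It applies only if the condition means the interaction, and its size (about 1.0 to 3.4 times for true effects of 1.2 down to 0.2 SD of change) rests wholly on assumed inputs. It is an average over significant trials and says nothing definite about any one estimate.

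**What to change.** In G.4, replace the conditional sentence with wording such as: *The model-estimated between-group differences in change from baseline to Week 5 and to Week 9 will be presented with 95% confidence intervals for each analysed PROMIS-29 T-score and for the MSQ total, whatever the result of the Group\*Visit test. Only that test governs a claim of statistical significance. The intervals are estimates not adjusted for multiplicity.*

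This also removes the mismatch between the interaction that is tested and the main effect named as the condition.

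The cost is one sentence and a few table rows from a model that is fitted anyway, with no added data, participants or procedures. The error rate of the significance claim is unchanged, because the test still governs it. The drawback is that some unadjusted intervals may exclude zero beside a non-significant overall test; the label is there to prevent their being read as findings.
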